5.3. Screening/Baseline/Run-In Failures

Screen failures are defined as subjects who consent to participate in the clinical trial but are never subsequently dosed. In order to ensure transparent reporting of screen failure subjects, meet the Consolidated Standards of Reporting Trials publishing requirements, and respond to queries from regulatory authorities, a minimal set of screen failure information is required including demographics, screen failure details, eligibility criteria, and serious AEs (SAEs).

5.4. Withdrawal/Stopping Criteria

The following actions must be taken in relation to a subject who fails to attend the clinic for a required study visit:

- The clinic must attempt to contact the subject and reschedule the missed visit as soon as possible.
- The site must counsel the subject on the importance of maintaining the assigned visit schedule and ascertain whether or not the subject wishes to and/or should continue in the study.
- In cases where the subject is deemed ‘lost to follow-up’, the investigator or designee must make every effort to regain contact with the subject (where possible, 3 telephone calls and if necessary a certified letter to the subject’s last known mailing address or local equivalent methods). These contact attempts should be documented in the subject’s medical record.
- Should the subject continue to be unreachable, only then will he/she be considered to have withdrawn from the study with a primary reason of “lost to follow-up”.

A subject may withdraw from study treatment at any time at his/her own request, or may be withdrawn at any time at the discretion of the investigator for safety, behavioral or administrative reasons. If a subject withdraws from the study, he/she may request destruction of any samples taken, and the investigator must document this in the site study records.

5.4.1. Liver Chemistry Stopping Criteria

Liver chemistry stopping and increased monitoring criteria have been designed to assure subject safety and evaluate liver event etiology in alignment with the FDA guidance, “Drug-Induced Liver Injury: Premarketing Clinical Evaluation,” [DHHS, 2009].

Study treatment will be stopped if the following liver chemistry stopping criterion is met:

- ALT $\geq 3 \times$ ULN

For details of the required assessments if a subject meets the above criteria, refer to [Appendix 2](#), Liver Chemistry Stopping Criteria.

5.4.2. QTc Stopping Criteria

- The same QT correction formula must be used for each individual subject to determine eligibility for and discontinuation from the study. This formula may not be changed or substituted once the subject has been enrolled.
 - For example, if a subject is eligible for the protocol based on the QTcF, then the QTcF must be used for discontinuation of this individual subject as well.
 - Once the QT correction formula has been chosen for a subject’s eligibility, the *same formula* must continue to be used for that subject *for all QTc data being collected for data analysis*. Safety ECGs and other non-protocol specified ECGs are an exception.
 - The QTc should be based on single or averaged QTc values of triplicate ECGs obtained over a brief (e.g., 5 to 10 minute) recording period.

A subject who meets either bulleted criterion below will be withdrawn from the study:

- QTc > 500 msec
- Increase from baseline of QTc > 60 msec

For subjects with underlying bundle branch block, the following discontinuation criteria will be used instead:

Baseline QTc With Bundle Branch Block	Discontinuation QTc With Bundle Branch Block
<450 msec	>500 msec
450 to 480 msec	≥ 530 msec

5.4.3. Gastrointestinal Stopping Criteria

Subjects experiencing Grade 3 or Grade 4 AEs (confluent pseudomembranes or ulcerations OR mucosal bleeding with minor trauma; tissue necrosis OR diffuse spontaneous mucosal bleeding OR life-threatening consequences, e.g., aspiration, choking) will be followed as appropriate until resolution of the AE(s).

Furthermore, subjects who experience diarrhea or enteritis should be evaluated with additional fecal occult blood tests and stool cultures as deemed appropriate by the investigator as outlined in [Appendix 8](#) and [Appendix 9](#).

For Part 3, subjects who experience diarrhea should also be evaluated using the guidelines detailed in [Table 8](#)

Table 8 Part 3 Management of Gastrointestinal Symptoms - Diarrhea

Diarrhea	Treatment Strategy
Grade 1	Initiate supportive care including loperamide.
Grade 2	Initiate supportive care including loperamide. Consider discontinuation of subject from the study upon discussion with medical monitor.
Grades 3 or 4	Above plus consider IV hydration, hospital admission and prophylactic antibiotics as appropriate. Withhold study drug(s) until diarrhea has resolved to ≤Grade 1, continue diarrheal prophylaxis. Discontinue subject from the study upon discussion with medical monitor.

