4.6.1. Risk Assessment

Potential Risk of Clinical Significance	Summary of Data/Rationale for Risk	Mitigation Strategy
Investigational Product Gepotidacin		
Gastrointestinal (GI) Effects	
Lower GI effects (soft stools, flatulence, and diarrhea) are the most common GI-associated adverse events (AEs) reported in human subjects dosed with gepotidacin. Additional events of heme + stool have been observed.
 
In the Phase I studies, out of approximately 400 healthy subjects who have received gepotidacin, Clostridium difficile has been reported in 8 subjects.
 
In an acute bacterial skin and skin structure infection study of 122 patients from 13 sites in the USA, the most frequently reported AEs were in the GI system including diarrhea, nausea, and abdominal cramping (see GlaxoSmithKline Document Number 2015N243789_00 Study ID BTZ116704). Events were usually mild in severity with fewer of moderate severity. No patients experienced severe GI AEs and none withdrew due to GI AEs.
	
Exclusion criterion and close monitoring of clinical parameters and AEs will be conducted to mitigate and assess GI effects.
 
Subjects with significant GI symptoms will obtain the appropriate work-up (Appendix 8).
 
Subject stopping criteria: Subjects experiencing Grade 3 or Grade 4 AEs will have permanent discontinuation of the investigational product and will be followed as appropriate until resolution of the AE.
 
For Part 3, subjects experiencing Grade 3 or Grade 4 diarrhea will be managed as described in Table 8

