Rash/Hypersensitivity	A fine, mild, generalized pruritic macular skin rash was seen in 3 of 8 subjects following 10 days of dosing 1500 mg 3 times daily (see GlaxoSmithKline Document Number 2014N198291_00 Study ID BTZ115198) Rash was reported as an AE for 4 of 122 subjects (3%) and consisted of mild, related urticaria; moderate, related rash maculopapular; mild, related rash; mild, related urticaria; and mild, not related arthropod bite (see GlaxoSmithKline Document Number 2015N243789_00 Study ID BTZ116704). There has been no other evidence of hypersensitivity in human subjects to date.	Exclusion criterion: History of sensitivity to any of the study drugs, components thereof, or a history of drug or other allergy that, in the opinion of the investigator or GlaxoSmithKline medical monitor, contraindicates their participation. Subject monitoring: Patients will be monitored closely for cutaneous effects throughout the study, and specialist advice will be sought as needed to evaluate any clinically significant finding. Subject stopping criteria: Grade 3 or higher rash or Grade 2 rash with evidence of systemic involvement.

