5.4.4. Rash/Hypersensitivity Stopping Criteria

A subject presenting with a Grade 3 AE or higher rash (diffuse macular, maculopapular, OR morbilliform rash with vesicles or limited number of bullae; OR superficial ulcerations of mucous membrane limited to 1 site) or a Grade 2 rash (diffuse macular, maculopapular, or morbilliform rash; OR target lesions) with evidence of systemic involvement will be followed as appropriate until resolution of the AE(s).

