Constipation	Requiring stool softener or dietary modification	Requiring laxatives	Obstipation requiring manual evacuation or enema	Obstruction or toxic megacolon
Diarrhea	Mild or transient; 3 to 4 loose stools/day or mild diarrhea lasting <1 week	Moderate or persistent; 5 to 7 loose stools/day or diarrhea lasting >1 week	>7 loose stools/day or bloody diarrhea; or orthostatic hypotension or electrolyte imbalance or >2L IV fluids required	Hypotensive shock or physiologic consequences requiring hospitalization
Oral discomfort/Dysphagia	Mild discomfort; no difficulty swallowing	Some limits on eating/drinking	Eating/talking very limited; unable to swallow solid foods	Unable to drink fluids; requires IV fluids

IV = intravenous.

NEUROLOGICAL				
	Grade 1	Grade 2	Grade 3	Grade 4
Neuro-cerebellar	Slight incoordination dysdiadochokinesis	Intention tremor, dysmetria, slurred speech; nystagmus	Locomotor ataxia	Incapacitated
Psychiatric	Mild anxiety or depression	Moderate anxiety or depression; therapy required; change in normal routine	Severe mood changes requiring therapy; or suicidal ideation; or aggressive ideation	Acute psychosis requiring hospitalization; or suicidal gesture/attempt or hallucinations
Muscle strength	Subjective weakness; no objective symptoms/signs	Mild objective signs/symptoms; no decrease in function	Objective weakness; function limited	Paralysis
Paresthesia (burning, tingling, etc)	Mild discomfort; no treatment required	Moderate discomfort; non- narcotic analgesia required	Severe discomfort; or narcotic analgesia required with symptomatic improvement	Incapacitating; or not responsive to narcotic analgesia
Neurosensory	Mild impairment in sensation (decreased sensation, e.g., vibratory, pinprick, hot/cold in great toes) in focal area or symmetrical distribution; or change in taste, smell, vision, and/or hearing	Moderate impairment (moderately decreased sensation, e.g., vibratory, pinprick, hot/cold to ankles) and/or joint position or mild impairment that is not symmetrical	Severe impairment (decreased or loss of sensation to knees or wrists) or loss of sensation of at least moderate degree in multiple different body areas (i.e., upper and lower extremities)	Sensory loss involves limbs and trunk; paralysis; or seizures

MUSCULOSKELETAL				
	Grade 1	Grade 2	Grade 3	Grade 4

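### Protocol Sections 4.6.1, 5.4.3 (with Table 8) and 5.4.4 do not give one consistent dosing action for severe GI events and stopping-level rash

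*Protocol*

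**What the plan says.** **GI events, Protocol Section 4.6.1.** The mitigation column states: "Subjects experiencing Grade 3 or Grade 4 AEs will have permanent discontinuation of the investigational product", with follow-up until resolution. It names no exception. The same cell then adds: "For Part 3, subjects experiencing Grade 3 or Grade 4 diarrhea will be managed as described in Table 8".

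**GI events, Protocol Section 5.4.3.** Under a heading that announces stopping criteria, subjects with Grade 3 or 4 events "will be followed as appropriate until resolution of the AE(s". No dosing action is given in that text.

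**Part 3 diarrhea, Table 8 in Section 5.4.3.** The Grade 3/4 cell carries down the rows above it, and the Grade 2 row asks only that discontinuation be considered. The cell then says "Withhold study drug(s) until diarrhea has resolved to ≤Grade 1, continue diarrheal prophylaxis". Its last sentence tells the site to discontinue the subject from the study upon discussion with the medical monitor.

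**Rash, Sections 4.6.1 and 5.4.4.** Section 4.6.1 lists as subject stopping criteria: "Grade 3 or higher rash or Grade 2 rash with evidence of systemic involvement". Section 5.4.4, also headed as stopping criteria, describes the same events and requires only that the subject be followed until resolution.

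**The concern.** A stopping rule has to tell the site whether the next dose is given. For a severe GI event the answer depends on where the reader looks: one section requires permanent discontinuation, another gives no dosing action, and the Part 3 table holds two instructions that point different ways. For rash, the events are labelled as stopping criteria in both places, but neither place spells out the stop.

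Two things are at stake. The first is the safety of healthy volunteers who, by Section 4.6.2, gain no direct benefit. The second is the make-up of the data. Part 3 gives active subjects 1500, 2250 and 3000 mg in that fixed order, so a decision after a severe event in Period 1 or 2 settles who supplies tolerability and PK data at the higher doses. Those observations feed the Part 3 power model and, at 3000 mg, the pooled Part 2 and Part 3 comparison in SAP Section 7.1.3.2.

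**Working it through.** The plan states no figure to reproduce here; the check is a comparison of the current text (Amendment 2).

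| Event | Place in protocol | Dosing action stated |
|---|---|---|
| Grade 3/4 GI event, all parts | 4.6.1 | Permanent discontinuation of product |
| Grade 3/4 GI event, all parts | 5.4.3 text | None; follow-up only |
| Grade 3/4 diarrhea, Part 3 | Table 8 | Withhold until Grade 1 or below; also discontinue upon discussion; Grade 2 wording (consider discontinuation) carried down |
| Grade 3+ rash, or Grade 2 with systemic involvement | 4.6.1 | Labelled a stopping criterion; action not spelled out |
| Same rash events | 5.4.4 | None; follow-up only |
| Liver criterion | 5.4.1 | Study treatment stopped |
| QTc criterion | 5.4.2 | Subject withdrawn |

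1. **Is there a later dose to decide about?** Yes. Section 4.1 sets three periods in Part 1a, two in Part 1b, two in Part 2 and three in Part 3. The remaining effect falls mainly on Part 3: Section 9.3.2 records that Part 1b is no longer needed, and Appendix 11 says Part 3 was added because of tolerability results already seen in Part 2.

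2. **What can withholding mean in Part 3?** Each period is one single dose. Once it is taken, the only drug left to withhold is the next period's dose, which for an active subject is higher. The washout is at least 3 days, so resolution to Grade 1 before that dose is possible. Withholding until resolution therefore reads as a condition for resuming, while the last sentence of the same cell ends participation.

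3. **Does the cross-reference in 4.6.1 settle it?** Only in part. It covers Part 3 diarrhea, leaves the permanent-discontinuation sentence unqualified, and leads to a cell that does not agree with itself. Other severe GI events in Part 3, and all severe GI events in other parts, remain under 4.6.1 and the 5.4.3 text.

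4. **Is the missing dosing action just house style?** No. Sections 5.4.1 and 5.4.2, in the same chapter, each state one.

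5. **Does anything say which section prevails?** No such rule appears in the protocol sections compared, and the SAP does not supply one.

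6. **Which data are affected?** After a severe event in Period 1, the decision governs both the 2250-mg and 3000-mg fed observations. After one in Period 2, it governs the 3000-mg observation.

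**The case against.** The strongest reply is that the passages can be read together. Following a subject is compatible with stopping the drug, so 5.4.3 and 5.4.4 are silent rather than contrary, and their headings signal a stop. Table 8 is a deliberate, cross-referenced exception. Its Grade 3/4 cell can be read in sequence as hold now, then discontinue after discussion, and it drops the Grade 2 qualifier that discontinuation is only to be considered. On that reading the outcome matches 4.6.1. There are also safeguards: investigator withdrawal for safety (5.4), the sentinel group and adverse-event review before each escalation (4.2), and the dose-escalation safety review (6.4).

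Much of this stands. The fault in 5.4.3 and 5.4.4 is an omitted stop statement, not an opposite instruction. The sequential reading of Table 8 is possible, but it leaves the condition about resolution to Grade 1 with no purpose and does not account for the Grade 2 wording carried down. The safeguards rest on judgment and do not replace a stated rule.

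Four stronger readings may tempt a reader, and the documents do not support them:

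- **That rash carries three conflicting actions.** Withholding never applies to rash; what is missing is the stop statement.
- **That different Part 3 sites could act in opposite ways.** Appendix 11 applies Amendment 2 to a single Part 3 site, so the exposure there is inconsistent handling between readers or subjects.
- **That the 5.4.3 descriptors, such as "confluent pseudomembranes or ulcerations OR mucosal bleeding with minor trauma", conflict with the Appendix 6 diarrhea row, ">7 loose stools/day or bloody diarrhea".** These describe different findings, and Appendix 6 itself lets protocol-specific grading override its tables.
- **That each affected subject costs a tenth of the 3000-mg fed sample.** One of the 10 planned active subjects is 10% arithmetically, but no event is shown to be expected, and Section 4.3 allows replacement.

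**Conclusion.** The inconsistency is real and should be corrected. It has two parts: the Table 8 Grade 3/4 cell disagrees with itself and sits beside an unqualified permanent-discontinuation sentence in 4.6.1, and Sections 5.4.3 and 5.4.4 lack the explicit dosing action that their headings and neighbouring sections lead a reader to expect.

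Its size cannot be put as a number. The documents give no expected rate of Grade 3 or 4 events in this setting and do not report the Part 2 results. Section 4.6.1 notes no severe GI events in an earlier study of 122 patients, so few or no subjects may be affected. The conclusion rests on two points: later doses are scheduled, and no precedence rule was found. It takes no position on which action is clinically right.

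**What to change.** Reconcile Section 4.6.1 (GI and rash rows), the text of 5.4.3, Table 8 and Section 5.4.4 so that each event and grade carries one action, worded the same way in each place. State the dosing action explicitly in 5.4.3 and 5.4.4. Make the two instructions in the Table 8 Grade 3/4 cell consistent with each other and with 4.6.1, including whether the Grade 2 wording is meant to carry down and whether the 4.6.1 sentence has a Part 3 exception. Clarify what the diarrheal prophylaxis to be continued refers to; the table mentions loperamide and prophylactic antibiotics but does not say which is meant. The choice of action belongs to the sponsor's clinicians.

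The cost is protocol wording in one amendment, with no added subjects, procedures or analyses.

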4.3. Type and Number of Subjects

For Part 1a, approximately 27 subjects will be enrolled with approximately 9 subjects in each of the 3 treatment sequences to ensure 24 PK parameter evaluable subjects with PK parameter estimates from the reference and at least one test formulation. For Part 1b, approximately 16 subjects will be enrolled with approximately 8 subjects in each of the 2 treatment sequences. For Part 2, approximately 10 Japanese subjects will be enrolled. For Part 3, approximately 12 Japanese subjects (ideally 6 male, 6 female) will be enrolled.

If subjects prematurely discontinue the study, additional subjects may be enrolled as replacement subjects and assigned to the same treatment sequence at the discretion of the sponsor in consultation with the investigator.

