Cardiovascular Effects Reversible increase in QT prolongation and a mild increase in heart rate in human subjects.	
In Study BTZ115775 [see GlaxoSmithKline Document Number 2015N227098_00 Study ID BTZ115775], the infusion of gepotidacin at a dose of 1000 mg and 1800 mg over 2 hours caused a mild heart rate effect of approximately 6 beats per minute to 10 beats per minute and a QT prolongation, measured as $\Delta\Delta QTcF$, of 12 msec to 22 msec. The QT prolongation evolved during the infusion and was quickly reversed over 2 hours after the end of the infusion. Blood pressure observations were within normal ranges.
 
The 1500 mg oral dose yields a Cmax of 4.8 μg/mL with predicted $\Delta\Delta QTcF$ (90% CI) of 7.5 msec (6.8 to 8.3 msec) compared with that observed after the therapeutic 1,000 mg intravenous (IV) dose (Cmax of 7.3 μg/mL) administered in the thorough QTc study.
	
Exclusion criteria, oral dosing of capsule and tablet formulations will have lower Cmax compared with IV doses in the thorough QTc study, close monitoring of clinical parameters, and AEs will be conducted and stopping criteria will be utilized to mitigate and assess cardiovascular effects.
 
Note: Subjects with a QRS duration <70 and >120 msec will be excluded.
 
Subject stopping criteria: Subjects experiencing a QTcB and/or QTcF >500 msec and/or a change from baseline in QTc >60 msec.

Potential Risk of Clinical Significance	Summary of Data/Rationale for Risk	Mitigation Strategy
Acetylcholinesterase (AChE) Inhibition In a mass spectrometry model performed with gepotidacin, AChE was inhibited with a concentration of inhibitor where the response (or binding) was reduced by half (inhibitory concentration) of approximately 5 µg/mL (7.5 µg/mL of total drug concentration).	At higher doses, some subjects have experienced effects consistent with increased cholinergic tone, including central nervous system and GI effects (including dizziness, abdominal pain, salivary hypersecretion, hot flush, diarrhea, fatigue, and nausea). These effects appear to be related to Cmax and are significantly attenuated when Cmax is below 14 µg/mL.	Coadministration of anticholinergics and administration in subjects with certain concomitant conditions will be excluded. Close monitoring of clinical parameters and AEs will be conducted to assess effects potentially related to AChE inhibition. The Cmax will be below 14 µg/mL in this study.

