6.4. Blinding

Parts 1 and 2 will be an open-label study.

Part 3 will be a double-blind (sponsor unblinded) study. The subjects will be completely blinded and the site staff will be blinded to subject-specific treatment assignment. The GSK study team will be unblinded at the aggregate level for decision making throughout the study (e.g. to support dose escalations and use of Bayesian predictive techniques).

Where possible, the GSK/clinical research organization personnel will not have access to subject-specific treatment assignment so as to not potentially introduce bias in discussions with the study site. The pharmacokineticists, statisticians, programmers, and data managers, however, will need access to subject randomization during the course of the study for analysis purposes to support dose adjustments and escalations. Other GSK staff may be included in discussions around dose adjustments and progression if it is deemed necessary and relevant by the above mentioned GSK study team members.

During dosing of a specific cohort, the investigator or treating physician may unblind a subject's treatment assignment only in the case of an emergency, when knowledge of the study treatment is essential for the appropriate clinical management or welfare of the subject. Whenever possible, the investigator must first discuss options with the GSK medical monitor or appropriate GSK study personnel before unblinding the subject's treatment assignment. If this is impractical, the investigator must notify GSK as soon as possible, but without revealing the treatment assignment of the unblinded subject, unless that information is important for the safety of subjects currently in the study. The date and reason for the unblinding must be recorded in the electronic data capture system. In this situation, the subject will be withdrawn from further treatment if the subject's treatment code is unblinded by the investigator or treating physician. The primary reason for discontinuation (the event or condition which led to the unblinding) will be recorded in the electronic data capture system. GSK's Global Clinical Safety and Pharmacovigilance staff may unblind the treatment assignment for any subject with an SAE. If the SAE requires that an expedited regulatory report be sent to 1 or more regulatory agencies, a copy of the report, identifying the subject's treatment assignment, may be sent to the investigator in accordance with local regulations and/or GSK policy.

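### Minor: the QTc rule and the Part 3 diarrhea guidance take a subject out of the study rather than off further dosing, so 48-hour PK sampling for a dose already taken may be cut short or lost

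*Protocol*

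**What the plan says.** All references are to the current protocol (Amendment 2) and the SAP.

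**Rules that remove the subject from the study**
- Protocol 5.4.2, QTc, is mandatory: "A subject who meets either bulleted criterion below will be withdrawn from the study".
- Protocol 5.4.3, Table 8, covers Part 3 diarrhea and is presented as guidance. For Grades 3 and 4 the cell first withholds drug until the diarrhea settles and then ends: "Discontinue subject from the study upon discussion with medical monitor". For Grade 2: "Consider discontinuation of subject from the study upon discussion with medical monitor".

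**Rules that stop treatment only**
- 5.4.1, liver: "Study treatment will be stopped if the following liver chemistry stopping criterion is met".
- 4.6.1, gastrointestinal row: "Subjects experiencing Grade 3 or Grade 4 AEs will have permanent discontinuation of the investigational product". The same row sends Part 3 Grade 3 or 4 diarrhea to Table 8.
- 6.4, after emergency unblinding: "the subject will be withdrawn from further treatment".

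**What happens afterwards**
- Sections 5.4 and 5.5 list no assessments for a subject removed under a stopping rule. Table 9 has no early-withdrawal column or footnote.
- Adverse events are followed up under 4.6.1, 5.4.3 and 7.3.1.3.
- Replacement is optional (4.3): "additional subjects may be enrolled as replacement subjects and assigned to the same treatment sequence at the discretion of the sponsor".
- SAP 10.5.1 uses whatever data exist for withdrawn subjects. It does not call for collection.

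**The concern.** Plasma and urine PK is the primary objective of Part 3, and AUC(0-∞), t1/2 and total urinary excretion all depend on samples out to 48 hours. With a half-life of about 12 hours (Tables 5 and 6), the full window spans about four half-lives; a stop at 12 hours spans one. The dose has been taken, the subject is resident and the samples are scheduled, so ending participation instead of dosing gives up data for no safety gain.

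The diarrhea case is foreseeable. Part 3 was added because of tolerability at 3000 mg fasted, and the same amendment brought in the diarrhea guidance (Appendix 11). If stopping tends to follow high exposure, the lost profiles would not be a random subset. Section 4.6.1 says of the cholinergic effects, which include diarrhea: "These effects appear to be related to Cmax". That is a link to Cmax, not to AUC, so any link to AUC is an assumption.

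**Working it through.** The plan gives no figure to reproduce. The calculations only size the effect.

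**Inputs**
- 10 active subjects in Part 3 (protocol 9.2.1).
- Between-subject CV of AUC(0-∞): 16.2% (fed RC tablet, Table 6) to 31.5% (3000-mg capsule, Table 7, N=6).
- Correlation r between stopping and log AUC: 0.3 to 0.5, assumed.

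**1. Profile lost altogether**

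SD of log AUC = sqrt(ln(1 + CV²)), which gives 0.161 and 0.308.

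Standard error of the log geometric mean with n = 10: 0.161/sqrt(10) = 5.1%; 0.308/sqrt(10) = 9.7%.

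Simulated change in the top-dose geometric mean when subjects drop out in order of a score correlated r with log AUC:

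| r | one lost, CV 16.2% / 31.5% | two lost, CV 16.2% / 31.5% |
|---|---|---|
| 0 | 0.0% / 0.0% | 0.0% / 0.0% |
| 0.3 | -0.8% / -1.6% | -1.5% / -2.9% |
| 0.5 | -1.4% / -2.6% | -2.5% / -4.8% |
| 1 (exactly the highest) | -2.7% / -5.1% | -5.0% / -9.3% |

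Every entry is below the standard error at the same CV.

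Precision also falls slightly. At an assumed within-subject CV of 22% to 27.5%, the 90% CI half-width for the Part 3 power-model slope goes from 0.241–0.300 to 0.250–0.311 if one 3000-mg profile is missing.

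**2. Profile kept but cut short**

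The illustrative fed profile rises linearly to Cmax 3.73 µg/mL at 3 h after a lag of 0 to 1 h. It then declines biexponentially with terminal half-life 11.7 h and AUC(0-∞) 16.9 µg·h/mL (Table 6). The slow-phase intercept is 5% to 17.5% of Cmax, and the fast-phase half-life is at least 0.4 h. Noncompartmental analysis used the scheduled times, linear-up/log-down, with the last three points for λz.

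| Sampling ends at | AUC(0-∞) for that subject, versus 48 h |
|---|---|
| 12 h | -2.9% to -18.2% |
| 24 h | 0.0% to -4.2% |
| 36 h | at most -1.0% |

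A 12-hour cut loses 3 of 13 post-dose plasma samples and 3 of 8 urine intervals. Estimated t1/2 then reads 2.3 to 10.7 h, against 11.4 to 11.7 h on the full schedule.

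Effect on the geometric mean of ten:
- 12 h: exp(ln(0.971)/10) - 1 = -0.3%, to exp(ln(0.818)/10) - 1 = -2.0%.
- 24 h, largest: exp(ln(0.958)/10) - 1 = -0.4%.

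Effect on the power-model slope for one 3000-mg profile, with centred log dose 0.327 and sum of squares 0.2425 per subject:
- 12 h, largest: 0.327 × ln(0.818)/(10 × 0.2425) = -0.027.
- 24 h, largest: 0.327 × ln(0.958)/2.425 = -0.006.
- Slope standard error at an assumed within-subject CV of 15% to 25%: 0.149/1.557 = 0.10 to 0.246/1.557 = 0.16.

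**3. How often the QTc rule should fire**

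Scaling the predicted effect in 4.6.1 linearly to the 3000-mg mean Cmax in Table 7: 7.5/4.8 × 9.03 = 14.1 msec, against a trigger above 60 msec. If it did fire, timing matters. As the broken Table 9 reads, an ECG falls at about 2 h, before the fed median Tmax of 3.0 h (range 1.5 to 4.0 h, Table 6), so Cmax could be lost too. Cuts at 12 h or later leave Cmax intact.

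**The case against.** The strongest reply is that completion is already required. Section 4.2 keeps subjects in the unit until Day 3 of the last period with scheduled PK and safety assessments done, and times the Follow-up visit from the final dose. Section 7 allows no waivers except for immediate safety concerns and makes adherence to Table 9 essential. Table 8 is guidance, and the discussion with the medical monitor is a natural moment to agree the remaining samples. This narrows the gap, and a site could well finish the period. But those passages are general and do not address a withdrawn subject, for whom leaving the study most naturally reads as the end of scheduled procedures. Sites could act differently.

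The SAP also has safeguards. Section 7.1.3.1 derives parameters only where the data permit and computes the percentage of AUC extrapolated. Section 7.1.3.2 analyses only if profiles are well defined and adds analyses without Grubbs outliers. Section 10.3.3 lists the points used for λz. These can flag or drop a heavily extrapolated profile, which limits the bias. They cannot recover uncollected samples.

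Two stronger readings are tempting and unsupported:
- A reader might infer that safety follow-up lapses at withdrawal. It does not: adverse events, including the cardiac and gastrointestinal risks in 4.6.1, must be followed. What is unsecured is mainly the remaining scheduled PK sampling.
- A reader might take the 18% figure as typical. It is the top of the range for a 12-hour cut, and the documents give no reason to expect 12 rather than 24 or 36 hours.

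**Conclusion.** The point stands as a minor, cheap improvement. Two rules remove a subject from the study where other rules stop treatment only, and no text secures the rest of the current period's PK schedule for that subject.

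The cost is a small avoidable loss of primary PK data. Whether the profile is lost or kept but cut, the shift in the geometric mean is below its standard error, including in the worst case where exactly the highest subjects are lost. The sizes rest on the assumed correlation, the CVs from earlier studies and an illustrative profile. The documents give no event probability for Part 3.

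A reader might infer that Part 3's PK or dose-proportionality conclusions are materially biased. The documents do not support that: Part 3 is sized on feasibility (9.2.1), no formal hypothesis is tested (9.1), and replacement is allowed, though discretionary.

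**What to change.** Keep every threshold. In 5.4.2 and in the Grade 2 and Grade 3/4 cells of Table 8, replace removal from the study with wording such as:

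*receives no further study treatment; completes the current period's PK blood and urine sampling and safety assessments to 48 h and the Follow-up visit, unless consent is withdrawn or the investigator judges it medically inadvisable.*

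Add a matching footnote to Table 9. Leave 5.4.1 and 6.4 unchanged.

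The cost is three wording changes, one footnote, and a few already-scheduled draws and collections in an affected subject. Sample size and analysis do not change. The gain is limited: later dose levels are not recovered, and the medical override will apply in some Grade 3 or 4 cases, where Table 8 itself envisages intravenous hydration or admission.
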